10. STUDY ENDPOINTS

10.1. Primary Endpoint

The primary endpoint is ORR, which is defined as the proportion of subjects with PR or CR according to RECIST 1.1. Subjects who discontinue due to toxicity or clinical progression prior to post-baseline tumor assessments will be considered as non-responders. Subjects who discontinue for reasons other than toxicity or clinical progression prior to the post-baseline tumor assessments or for other reasons prior to their first dose of study drug will be replaced and not included in the primary efficacy analysis.

10.2. Secondary Endpoint

The secondary endpoint is as follows:

Safety assessed by the following measures:

- Number of patients who have grade 3 or higher drug-related toxicities
- Frequency of drug-related toxicity by grade
- Nivolumab- and relatlimab-related infusion reactions
- Immune-related AEs
- Unacceptable toxicities
- Vital signs: BP, pulse, respiratory rate, temperature
- Physical examination
- Changes in ECG readings
- Clinical hematology: complete blood count (CBC) with differential ANC, ALC, AEC, and platelet count
- Clinical serum chemistry: sodium, potassium, chloride, bicarbonate, glucose, BUN, creatinine, LDH, ALT, AST, alkaline phosphatase, total bilirubin, direct bilirubin, amylase, lipase, total protein, albumin, calcium, magnesium, and phosphorus
- TSH, T3, Free T4
- Cardiac troponin

10.3. Exploratory Endpoints

Exploratory endpoints are as follows:

- Overall survival (OS), progression free survival (PFS), time to-progression (TTP), disease control rate (DCR), best overall response (BOR), duration of response (DOR), duration of clinical benefit (DCB), and time to objective response (TTOR) measured by RECIST 1.1 (Appendix C).
 - Overall survival (OS) is defined as the number of months from the date of first treatment until death or end of follow-up (OS will be censored on the date the subject was last known to be alive for subjects without documentation of death at the time of analysis).
 - Progression-free survival (PFS) is defined as the number of months from the date of first treatment to disease progression (PD or relapse from CR as assessed using

RECIST 1.1 criteria) or death due to any cause. PFS will be censored at the date of the last scan for subjects without documentation of disease progression at the time of analysis. iPFS is defined as the time to iUPD if the next scan (4-8 weeks later) confirms PD (state change from iUPD to iCPD, time to progression defined in this instance as iUPD).

- Disease Control Rate (DCR) is defined as the percentage of subjects achieving stable disease or better (SD + PR + CR).
- Best Overall Response (BOR) is defined in **Appendix C.**
- Duration of Response (DOR) is defined as the number of months from the first documentation of a response to date of disease progression.
- Duration of Clinical Benefit (DCB) is defined as the number of months from the date of first treatment to date of disease progression in those achieving a PR or CR.
- Time to Objective Response (TTOR) is defined as the number of months from the date of first treatment to the date of documented partial or complete response.
- Time to-progression (TTP) is defined as the number of months from the date of first treatment to the date of documented disease progression (PD or relapse from CR as assessed using RECIST 1.1 criteria). It differs from PFS in that it does not include death in the definition of an event. TTP will be censored at the date of the last scan for subjects without documentation of disease progression at the time of analysis.
- iORR by immune-related RECIST criteria (iRECIST).
- Immune subset analysis by IHC and gene expression profiling of the tumor
 - Sequencing of tumor
 - Assessment of tumor burden dynamics using standard protein biomarkers when available as well as circulating biomarkers (i.e. ctDNA).
 - Immune subset analyses by FACS in PBMCs including effector, helper, and regulatory T cells, NK cells and macrophages
 - T cell receptor (TCR) repertoire analysis in PBMCs and tumors
 - Gene expression analysis of PBMCs
 - Microbial community analysis and whole metagenome functional profiling analysis of stool and oral wash samples.

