4.12.3 Survival Follow-up

Subjects who discontinue treatment and have disease progression will enter the survival follow-up portion of the trial. Subjects should be contacted every 12 weeks (\pm 2 weeks) to monitor overall survival. Information of other cancer therapies after discontinuation from the study treatment will be collected as well.

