The primary endpoint is objective response rate, defined as complete response (CR) or partial response (PR) per RECIST 1.1. Objective response rate (ORR) will be estimated as the proportion of subjects whose best overall response is either a CR or PR with corresponding 95% CI. The primary population for the analysis is all subjects who receive at least one dose of study drug, and have at least one post-baseline tumor assessments or discontinue due to toxicity or clinical progression prior to post-baseline tumor assessments.

Exploratory endpoints include progression-free survival (PFS), overall survival (OS), and duration of response (DOR). PFS is defined as the time from the first day of study treatment to the date of the first documented tumor progression or death due to any cause, whichever occurs first. Subjects who did not progress or die will be censored on the date of their last tumor assessment. Kaplan-Meier curves will be used to summarize PFS. Overall survival (OS) is the time from the first day of study treatment to the date of death due to any cause. A subject who has not died will be censored at last known date alive. Kaplan-Meier curves will be used to summarize OS. Among patients with an objective response, DOR is defined as the time between the date of initial complete or partial response to the date of the first documented tumor progression or death due to any cause. Subjects who neither progress nor die will be censored on the date of their last tumor assessment. Summary statistics will be presented for DOR.

For biomarkers, potential relationships between biomarker data and efficacy or safety endpoints will be investigated aimed at identifying baseline biomarkers that may be used to prospectively identify subjects likely (or not likely) to respond to the treatment and to identify subjects who may be predisposed to having adverse reactions to treatment. These exploratory biomarker analyses will be completed with biomarkers measured in blood and in tumor samples.

The performance of the PD-L1/mucin composite score (CPM) in predicting treatment response will be further evaluated. ROC analysis based on logistic regression will be used to assess the

prediction accuracy, and the cutoff threshold for identifying patients who may benefit the therapy will be validated.

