APPENDIX D: DESCRIPTION OF THE IRECIST PROCESS FOR ASSESSMENT OF DISEASE PROGRESSION

Assessment at Screening and Prior to RECIST 1.1 Progression

Until radiographic progression based on RECIST 1.1, there is no distinct iRECIST assessment.

Assessment and Decision at RECIST 1.1 Progression

In participants who show evidence of radiological PD by RECIST 1.1 the Investigator will decide whether to continue a participant on study treatment until repeat imaging is obtained using the criteria outlined in **Section 4.10.1**.

If the Investigator decides to continue treatment, the participant may continue to receive study treatment and the tumor assessment should be repeated 4 to 8 weeks later to confirm PD by iRECIST, per Investigator assessment.

Tumor flare may manifest as any factor causing radiographic progression per RECIST 1.1, including:

- Increase in the sum of diameters of target lesion(s) identified at baseline to \geq 20% and > 5 mm from nadir
 - Please note: the iRECIST publication uses the terminology "sum of measurements", but "sum of diameters" will be used in this protocol, consistent with the original RECIST 1.1 terminology.
- Unequivocal progression of non-target lesion(s) identified at baseline
- Development of new lesion(s)

iRECIST defines new response categories, including **iUPD** (unconfirmed progressive disease) and **iCPD** (confirmed progressive disease). For purposes of iRECIST assessment, the first visit showing progression according to RECIST 1.1 will be assigned a visit (overall) response of iUPD, regardless of which factors caused the progression.

At this visit, target and non-target lesions identified at baseline by RECIST 1.1 will be assessed as usual.

New lesions will be classified as measurable or non-measurable, using the same size thresholds and rules as for baseline lesion assessment in RECIST 1.1. From measurable new lesions, up to 5 lesions total (up to 2 per organ), may be selected as New Lesions – Target. The sum of diameters of these lesions will be calculated, and kept distinct from the sum of diameters for target lesions at baseline. All other new lesions will be followed qualitatively as New Lesions – Non-target.

Assessment at the Confirmatory Imaging

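### iPFS counts first progression as an event only if the next scan confirms it, but patients who stop treatment at progression will often have no such scan, so iPFS is biased upward

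*Combined protocol and SAP*

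**What the plan says.** The only definition of iPFS is in Section 10.3, inside the PFS bullet: "iPFS is defined as the time to iUPD if the next scan (4-8 weeks later) confirms PD". A parenthesis adds that the progression date is then the iUPD date. The sentence says nothing about death, about an iUPD with no later scan, or about censoring.

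The neighbouring definitions are more complete. PFS ends at progression by "RECIST 1.1 criteria) or death due to any cause". For TTP the text is explicit: "It differs from PFS in that it does not include death in the definition of an event". The censoring rule in the bullet is worded for PFS: "PFS will be censored at the date of the last scan for subjects without documentation of disease progression at the time of analysis". Section 12.1 repeats PFS as time to the "date of the first documented tumor progression or death due to any cause, whichever occurs first" and does not mention iPFS.

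The imaging path after first progression is set in four places:

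- **Appendix D:** at RECIST 1.1 progression, "the Investigator will decide whether to continue a participant on study treatment until repeat imaging is obtained". If treatment goes on, the "participant may continue to receive study treatment and the tumor assessment should be repeated 4 to 8 weeks later to confirm PD by iRECIST".
- **Section 4.10.1:** treatment past progression is for patients without symptoms or signs of progression who have investigator-assessed benefit and tolerate the drug.
- **Section 4.12.3:** subjects who stop treatment and "have disease progression will enter the survival follow-up portion of the trial". The calendars in Sections 9.1 and 9.2 mark no CT/MRI in that period.
- **Section 9 footnotes 15 and 22:** the end-of-treatment (EOT) scan falls 30 days (± 4 weeks) after the final dose and need not be repeated if a scan was done in the past 6 weeks.

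**The concern.** The rule makes an event depend on a later scan, and the protocol directs that scan mainly to patients judged fit to continue. A patient who progresses, deteriorates and stops will often have no confirming scan and so, on the literal wording, no event. The loss is informative: it is caused by the event itself and is concentrated in the patients doing worst.

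This trial permits treatment beyond progression, so iPFS longer than PFS could be read as delayed immune benefit. Some of that gap may be real, because pseudo-progression is properly not an iPFS event. Another part would come from the definition alone, and the two could not be separated.

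**Working it through.** **No plan figure to reproduce.** The documents give no median, event count or power for iPFS. The check is whether the confirming scan can be expected, and then what its absence does to the estimate.

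**1. Does the EOT scan supply the confirmation?**
Inputs (Section 9): dosing on day 1 of 28-day cycles, so at weeks 0, 4, 8, 12 and so on; scans at week 12, every 8 weeks to week 52 (20, 28, 36, 44, 52), then every 12 weeks (64, 76 and so on). Every scan week is a multiple of 4. With no delays, a patient stopped on a scheduled progression scan had the last dose either 28 days before the scan or at about the same time.
- Last dose 28 days before: nominal EOT scan is 30 − 28 = 2 days after the progression scan.
- Last dose at the scan: nominal EOT scan is 30 days after it.

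Both are under 6 weeks (42 days), so at the nominal date the waiver applies. The EOT scan may still be done, but the plan does not require it.

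**2. Size in the simplest model.**
Assumptions: constant hazard, true median to first iUPD of 3 months, and a fraction f of first progressions never confirmed and censored at that scan. The estimated hazard is multiplied by (1 − f), so the apparent median is 3/(1 − f):
- f = 0.30: 3/0.70 = 4.3 months
- f = 0.45: 3/0.55 = 5.5 months
- f = 0.60: 3/0.40 = 7.5 months

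**3. Size on the protocol's scan grid.**
Assume a 13-week median, so the weekly hazard is ln 2/13 = 0.0533. The chance of progression by week 12 is 1 − exp(−0.0533 × 12) = 0.473. From week 12 to 20, among those still free of progression, it is 1 − exp(−0.0533 × 8) = 0.347. Under the literal rule, with deaths also censored, 26-week iPFS is [1 − 0.473(1 − f)] × [1 − 0.347(1 − f)]:

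| f | 26-week iPFS |
|---|---|
| 0 | 0.34 |
| 0.2 | 0.45 |
| 0.4 | 0.57 |
| 0.6 | 0.70 |
| 0.8 | 0.84 |

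If every unconfirmed iUPD and every death is an event, the f = 0 value is multiplied by survival from death to 26 weeks. With death assumed to be 5% of the total hazard, that is 0.344 × exp(−26 × 0.0533 × 0.05/0.95) = 0.32. At 15% it is 0.344 × exp(−26 × 0.0533 × 0.15/0.85) = 0.27. A simulation of 200,000 patients per scenario gave the same values.

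Over assumed medians of 8.7 to 26 weeks and both death shares, 40% never re-scanned raised simulated 26-week iPFS by about 17 to 31 percentage points. It left about 15 to 18 events in 32 patients, against 32 under the corrected rule with full follow-up.

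**4. How much is due to death?**
With every patient re-scanned, leaving death out raised 26-week iPFS by only about 2 to 7 points. If death does count but un-rescanned iUPD is still censored, then at f = 0.4 and a 13-week median the result is 0.53 (5% death share) or 0.44 (15%). Against 0.32 and 0.27, that is still 21 and 17 points too high. Missing confirmation is the main driver.

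**5. Conflict over which scan confirms.**
Section 10.3 looks only to the next scan at 4-8 weeks. Appendix D lets an iUPD persist and be confirmed at a subsequent scan. On Section 10.3's wording, such a patient has a confirmed progression (iCPD) but no iPFS event. After week 52, routine scans are also 12 weeks apart, outside the 4-8 week window unless the extra scan that Appendix D describes is done.

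**The case against.** The strongest reply is that the plan never says that deaths are not iPFS events. A reader might infer this from the sentence read alone, but the documents do not support it as a stated rule. The sentence sits in the PFS bullet directly after death is named, its parenthesis can be read as re-dating only the progression component, and where the authors exclude death, for TTP, they say so. This stands: for death the text is ambiguous, not wrong. It does not rescue the definition, because carrying death over still leaves an un-rescanned iUPD without an event at its own date. Carrying over the PFS censoring rule does not settle it either, since that rule is for patients without documented progression and these patients have one under RECIST 1.1.

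A reader might also infer that nobody who stops at progression is scanned again. That goes too far. The EOT scan is scheduled and only waivable, and treatment past progression with re-imaging is allowed, so the unconfirmed share is unknown.

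The medians rest on assumed inputs. The simple formula ignores the scan grid: at 60% never re-scanned it gives 7.5 months, while the grid calculation with a 13-week median gives 44 weeks, about 10 months. Neither modelled pseudo-progression. The direction stands; no single figure should be read as this trial's bias.

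Finally, iPFS is not named in the objectives (Section 1.3), has no analysis in Section 12.1, and no comparison with PFS is planned. That limits the consequence. Appendix D also refers to the iRECIST publication for further detail, but an endpoint definition should not depend on a source outside the plan.

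**Conclusion.** The concern holds in limited form. As written, the iPFS rule drops progressions that the protocol's own imaging path often leaves unconfirmed, and nothing in Section 12.1 repairs it. The bias is upward relative to PFS and falls on patients who tend to be doing worst. Its size cannot be taken from the documents; the figure of 4.3 to 7.5 months against a true 3 rests on an assumed constant hazard, an assumed median and an assumed 30% to 60% unconfirmed. The handling of death is unstated, and the reference to the next scan conflicts with Appendix D.

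A reader might infer that the trial's conclusions are at risk. They are not: ORR, the two-stage go/no-go rule, the sample size and RECIST 1.1 PFS do not use iPFS. This is a correction to an exploratory endpoint, worth making because it is cheap and because iPFS is easily over-read in an immunotherapy trial.

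**What to change.** Replace the iPFS sentence in Section 10.3 with a full definition: time from first dose to the earliest of

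- (a) the first iUPD of an episode later confirmed as iCPD at any subsequent scan, dated at that first iUPD;
- (b) an iUPD episode with no later assessment, or one that stays iUPD without resolving through the last assessment, dated at the first iUPD of that episode;
- (c) death from any cause.

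An iUPD that resolves to iSD, iPR or iCR is not an event. All other patients are censored at the last tumor assessment. Dating (b) at the start of the episode keeps it consistent with (a) when iUPD persists over several scans.

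If iPFS will be reported, name it in Section 12.1 with the same definition. The cost is a few lines of text, settled before the data are analysed. The definition uses data already collected, adds no scans and leaves patient management unchanged.

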11.1. Data Collection and Processing

All information will be collected on study-specific CRFs by study staff. These data will be reviewed for completeness and accuracy by the Principal Investigator at each site.

CRFs will be used to capture study results and data. The study coordinator or other authorized study personnel will transcribe data from source documents onto eCRFs. Before or between visits, the IND Sponsor, or designee may request copies of the CRFs for preliminary medical review. Once the CRFs are complete and source-verified, the investigator must sign and date all required pages, verifying the accuracy of all data contained within the CRF.

11.2. Safety Meetings

Scheduled meetings will take place weekly and will include the protocol principal investigator, study coordinator(s), data manager(s), sub-investigators (as appropriate), collaborators (as appropriate), and biostatisticians (as appropriate) involved with the conduct of the protocol. During these meetings matters related to the following will be discussed: safety of protocol participants, validity and integrity of the data, enrollment rate relative to expectation, characteristics of participants, retention of participants, adherence to protocol (potential or real protocol violations), data completeness, and progress of data for objectives.

11.3. Monitoring

The SKCCC Compliance Monitoring Program will provide external monitoring for JHU-affiliated sites in accordance with SKCCC DSMP (Version 6.0, 02/21/2019). The SMC Subcommittee will determine the level of patient safety risk and level/frequency of monitoring. The PI shall internally monitor the progress of the trial, including review and confirmation of all safety/treatment-related outcomes, response assessments, safety reports and/or any related source documentation. The protocol will be monitored externally by the SKCCC CRO QA Office. Additional data and safety monitoring oversight will also be performed by the SKCCC Safety Monitoring Committee (SMC - as defined in the DSMP).

[name] is holding the IND for this study. She will comply with all regulated reporting requirements to the FDA.

11.4. Study Documentation

11.4.1 Informed Consent and Authorization for use and Disclosure of Protected Health Information

Written informed consent and authorization of use and disclosure of protected health information (PHI) must be obtained from each subject (or the subject's legally authorized representative) before performing any study-specific screening/baseline period evaluations. The ICF and authorization for use and disclosure of PHI, which is prepared by the investigator or the site, must be reviewed and approved by the IND Sponsor, the study monitor (if applicable), and the site's IRB before the initiation of the study.

11.4.2 Investigator Study Files

Documentation about the investigator and study staff, the IRB and the institution, is required before study site initiation. A list of required documents will be provided by the

IND Sponsor or designee to each participating investigator. Copies of these documents as well as supplemental information, such as the investigator's obligations, IB, clinical study protocol and amendments, safety information, investigational agent information, biological samples and laboratory procedures, SRM, study logs and IND Sponsor/investigator/study monitor correspondence will be kept on-site in study site-specific binders.

The IND Sponsor or designee will be responsible for maintaining original and backup of all CRF data. The investigator is responsible for maintaining backup of all electronic data systems used for primary documentation or source documentation. Backup of electronic data will be performed periodically as described in the site-specific SOPs. Backup records must be stored at a secure location on site and backup and recovery logs must be maintained to facilitate data recovery. If an electronic medical records system that is not supported by the IND Sponsor or designee (or is discontinued or decommissioned) is used, the investigator must maintain a system to retrieve these records or arrange for the transfer of these records to an alternate electronic format or to paper.

Changes to any electronic records require an audit trail, in accordance with 21 CFR 11.10(e), and should include who made the changes and when and why the changes were made. An audit trail is defined as a secure, computer-generated, time-stamped electronic record that will allow reconstruction of the course of events relating to the creation, modification and deletion of an electronic record. Audit trails must be created incrementally, in chronological order and in a manner that does not allow new audit trail information to overwrite existing data. Audit trails should be in a readable format and readily available at the study site and any other location where electronic study records are maintained.

Audit trails are generated automatically for eCRFs. The investigator is responsible for maintaining audit trails of all electronic data systems used for primary documentation or source documentation.

11.4.3 Case Report Forms and Source Documentation

The investigator must make study data accessible to the site monitor, to other authorized representatives of the IND Sponsor (or designee) and to the appropriate regulatory authority inspectors. The original CRF for each subject will be checked against source documents at the study site by the site monitor.

